# 4.1.1.5 Sensitivity Analyses

Sensitivity analyses to assess the impact of missing data on the study's estimates will be performed. In addition, sensitivity analyses may also be conducted to examine the extent to which changes in certain methods or assumptions affect the results, for example excluding from the analysis patients with history of another primary malignancy. All sensitivity analyses will be fully outlined in the SAP.

## 4.1.2 Analysis Plan for Primary Objective

The primary outcome of this study, DFS, will be estimated and plotted using the KM estimator for up to 42 months follow-up.

• Median DFS and the corresponding two-sided 95% CIs will be estimated.

## 4.1.3 Analysis Plan for Secondary Objectives

## 4.1.3.1 Secondary Effectiveness Outcomes

The analysis of OS and DMFS for all nivolumab patients and OS and PFS2 for patients that receive subsequent treatment following nivolumab treatment discontinuation will be performed following a similar procedure as for DFS (see Section 4.1.2) and will be estimated and plotted using the KM estimator overall and by subgroup of interests.

- Median DFS in subgroup of interest (overall DFS is assessed a primary outcome) and DFS rates will be estimated and reported along with the corresponding two-sided 95% Cis
- Median OS with the corresponding two-sided 95% CIs will be reported. OS rates will be estimated and reported along with the corresponding two-sided 95% CIs.

- Median DMFS and the corresponding two-sided 95% CIs will be estimated. DMFS rates will be estimated and the corresponding two-sided 95% CIs will be reported.
- Median PFS2 and the corresponding two-sided 95% CIs will be estimated. PFS2 rates will be estimated and the corresponding two-sided 95% CIs will be reported.
- Median ORR the corresponding two-sided 95% CIs
- Where adequate follow-up data is available median DFS, OS, PFS2, DMFS and ORR with their corresponding two-sided 95% CIs will be estimated in subgroup of interests (see section 4.1.1.4) as described for the overall population.

## 4.1.3.2 Disease Recurrence Patterns

Descriptive statistics will be used to summarize the characteristics of patients with a recurrence, notably the type of recurrence (local/regional vs. metastatic) and the subsequent treatments after recurrence. PRS will be estimated as described in Section 4.1.2 for patients with recurrent EC of GEJC and the corresponding two-sided 95% CIs will be reported.

Where adequate follow-up data is available, the above outcomes will be estimated for the subgroups detailed in the SAP.

### 4.1.3.3 Patient Management and Treatment Patterns

Descriptive statistics will be used to summarize patient management and treatment patterns.

- Cancer treatment history for EC or GEJC prior initiation of nivolumab will be summarized descriptively.
- Nivolumab treatment characteristics including duration, frequency, dosing, interruptions, permanent discontinuations of nivolumab, factors associated with the initiation and/or discontinuation of nivolumab, reasons for discontinuations, modifications in relation to the management of AEs and time-to-treatment discontinuation will be summarized using descriptive statistics
- Subsequent treatment characteristics including type of treatment, duration, frequency, dosing, TTNT, will also be summarized descriptively.

## 4.1.3.4 Sociodemographic and Clinical Characteristics

All baseline data (i.e., sociodemographic, disease characteristics, comorbidities, concomitant treatments, disease history, concurrent medical conditions, prior treatments for EC/GEJC, cancer diagnosis, and laboratory data) will be summarized overall and by subgroup of interests, using standard descriptive analyses as described in Section 4.1.1.

### 4.1.3.5 Nivolumab Related Adverse Events

All treatment-related AEs will be coded by severity grade. Descriptive statistics will be used to describe the frequency and severity of select AEs, other immune-related AEs, and other

treatment-related AEs and toxicities. The incidence will be calculated as the number of patients with AEs divided by total patients. AEs by subgroup of interests will be described; however, it is anticipated that the analysis will be limited by sample size.

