Among patients who received nivolumab, the median DFS was doubled as compared with patients who received placebo: 22.4 months (95% confidence interval [CI] 16.6 to 34.0) vs. 11.0 months (95% CI 8.3 to 14.3). The hazard ratio for disease recurrence or death was 0.69 (96.4% CI 0.56 to 0.86; p<0.001). The efficacy of nivolumab compared with placebo was observed across multiple prespecified subgroups based on demographic and baseline disease characteristics, including age group ( $\geq$ 65 and <65), sex, race, region, disease stage at diagnosis (II and III), histologic type (SCC and adenocarcinoma), and tumor cell PD-L1 expression. More than half of the trial patients had lymph node-positive disease at baseline and, despite the poor prognosis in these patients, nivolumab was associated with improvement in DFS, with a 31% reduction in the risk of recurrence or death.

The safety profile of nivolumab was consistent with those observed in previous trials in patients with gastroesophageal and other solid tumors. Grade 3 or 4 adverse events (AE) that were considered by the investigators to be related to the trial regimen were more common in the nivolumab group (in 71 of 532 patients [13%]) compared with the placebo group (in 15 of 260

patients [6%]). The most common grades 3 or 4 select treatment-related AEs (TRAEs) in the nivolumab group were pneumonitis (in four patients [<1%]) and rash (in four patients [<1%]). In the placebo group, each of these AEs was observed in one patient each (<1%). The most common AEs of any grades that were classified as related to the trial regimen by the investigators were fatigue, diarrhea, pruritus, and rash in the nivolumab group and diarrhea and fatigue in the placebo group.

Based on the results of CheckMate 577 trial, in May 2021 and July 2021, the Food and Drug Administration (FDA) and European Commission, respectively, approved nivolumab for patients with resected EC or GEJC with residual pathologic disease who have received neoadjuvant chemoradiotherapy.

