#### **Treatment-related Adverse Events**

Treatment-related AEs are those events with a relationship to the study drug recorded as "Related" on the eCRF.

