#### **Immune-related Select Adverse Events**

Among the immune-related AEs, a category of "select AEs" will be created to group the most common and impactful AEs, providing a better estimate of the frequency of similar types of organ-related AEs. These select AEs are further defined as follows:

- May differ from or be more severe than AEs caused by non-immunotherapies
- May require unique (non-standard) intervention such as immuno-suppressants (or hormone replacement therapy)
- Early recognition and management may mitigate severe toxicity

"Select AEs" category:

- Pneumonitis
- Diarrhea/Colitis
- Hepatitis
- Nephritis and renal dysfunction
- Endocrinopathies

- Pruritus
- Rash
- Severe infusion reactions

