### **Other Immune-Related AEs**

In this study, immune-related AEs are defined as nivolumab treatment-related AEs that are consistent with the immune-based mechanisms of action of nivolumab, per investigator-assessed causality, and can occur during or after nivolumab treatment. Select AEs are special group of AEs, which follow the criteria listed above. Immune-related AEs that are not categorized as select AEs are considered as other immune-related AEs. Other immune-related AEs may include:

- Myocarditis
- Arthralgias
- Uveitis
- Pancreatitis
- Demyelination
- Guillain-Barre Syndrome
- Myasthenic syndrome
- Encephalitis

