## 4 STATISTICAL ANALYSIS

## 4.1 Statistical Analysis Methods

## 4.1.1 General Aspects

This study is purely descriptive, and no formal hypotheses will be tested. An overview of planned statistical analyses is provided in Sections 4.1.1 to 4.1.4. A standalone statistical analysis plan (SAP) will describe in detail all planned statistical analyses to be performed for this study.

The SAP will include tables, listings, figure shells to be populated during the interim and final data analyses, and details of changes in the planned analysis post-protocol finalization if applicable. It will also provide a description of the methods to deal with missing data, censoring, and procedures to control for potential sources of bias and their influence on the results.

All analyses will be conducted in accordance with the study objectives, SAP, and applicable guidelines. Statistical methods will be driven, in part, by the final sample size and the number of events. Results will be rounded to one decimal place; therefore, percentages may not always add up to 100. Standard deviation and 95% CIs will be calculated when relevant. The statistical analyses will be performed using SAS enterprise 7.1 or above, or SAS 9.4 or above. All patients who meet eligibility criteria will be included in the analysis data set.

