#### Adverse Events Collected for this Study

Serious and non-serious AEs:

- Related AEs (adverse drug reactions) should be reported without time limitation
- Non-related AEs should be reported until 100 days after the last administration of nivolumab.

Although not always AEs by regulatory definition, the following events associated with a BMS product must be reported:

- Any occurrence of a possible exposure of a pregnant woman to a product (this could involve a patient or the partner of a male patient or a pregnant female who came in contact with the medication while dispensing) or exposure (to infant) during lactation.
- All reports of elevated/ questionable or indeterminate beta human chorionic gonadotropin or positive urine pregnancy tests after administration of a product
- Exposure (to fetus) during pregnancy, exposure (to infant) during lactation, and paternal exposure
- Overdose
- Lack of efficacy
- Abuse
- Misuse
- Off-label use

- Occupational exposure
- Medication error and potential medication error
- Suspected transmission of an infectious agent, e.g., any organism, virus or infectious particle pathogenic or non-pathogenic, via the medicinal product
- Unintended benefit.

The AEs under study require a causal assessment.

The causal relationship to the BMS product under study is determined by a physician and should be used to assess all AEs under study. The causal relationship should be one of the following:

- Related: There is a reasonable causal relationship between the BMS product under study and the AE.
- Not related: There is not a reasonable causal relationship between the BMS product under study and the AE.

The term "reasonable causal relationship" means there is evidence to suggest a causal relationship.

A non-serious AE is an AE not classified as serious.

An *SAE* is any untoward medical occurrence that at any dose:

- 1. Results in death
- 2. Is life-threatening (defined as an event in which the patient was at risk of death at the time of the event; it does not refer to an event which hypothetically might have caused death if it were more severe)
- 3. Requires inpatient hospitalization or causes prolongation of existing hospitalization. The following hospitalizations are not considered SAEs in BMS studies:
  - A visit to the emergency room or other hospital department < 24 hours, that does not result in admission (unless considered an important medical or life-threatening event).

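### Select-AE categories and the committed severity grading depend on the physician marking an event as nivolumab-related; in a single-arm study an all-cause graded table should stand beside them

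*Protocol*

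**What the plan says.** All references are to the Protocol.

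- **Relatedness.** Section 3.5.1.4: "Treatment-related AEs are those events with a relationship to the study drug recorded as" related on the eCRF. Section 7: "The causal relationship to the BMS product under study is determined by a physician", with two options, related or not related.
- **Immune-related AEs.** Section 3.5.1.4: "immune-related AEs are defined as nivolumab treatment-related AEs that are consistent with the immune-based mechanisms of action of nivolumab, per investigator-assessed causality".
- **Select AEs.** Section 3.5.1.4 builds them inside that class ("Among the immune-related AEs, a category of" select AEs is created). The list includes pneumonitis, diarrhea/colitis, hepatitis and rash. The stated aim is "providing a better estimate of the frequency of similar types of organ-related AEs".
- **Grading.** Section 4.1.3.5: "All treatment-related AEs will be coded by severity grade". Frequency and severity are then described for select, other immune-related and other treatment-related AEs.
- **Non-related events.** Section 7 collects them until 100 days after the last nivolumab dose; related events have no time limit. Section 7.1.1 promises aggregate reporting of all AEs, labelled by relatedness where data collection allows.
- **Denominator.** Section 4.1.3.5 divides by total patients. Section 4.1.1 says "All patients who meet eligibility criteria will be included in the analysis data set".

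**The concern.** An event must be marked as related before it can enter a select-AE table, and related events are the only ones for which a severity grade is promised. A pneumonitis or colitis marked as not related is still collected, but it leaves the category that is supposed to estimate how often that organ event occurs.

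The study has one cohort. Patients come to nivolumab after surgery and, under the approved indication described in section 1.1, after chemoradiotherapy, so other explanations for an organ event are often available. No control arm shows how far attribution reflects the drug and how far it reflects the physician.

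This matters most for section 4.1.1.4. It plans to compare CheckMate 577-like patients with the rest on safety as well as effectiveness, and says that similar outcomes would support use in nearly all patients with these cancers. If physicians attribute events differently in the two groups, similarity or difference in related-only rates is partly a statement about attribution.

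**Working it through.** **1. The nesting.** Set side by side, the definitions in section 3.5.1.4 give: select AE ⊂ immune-related AE ⊂ AE recorded as related. Section 4.1.3.5 commits grading to the outermost of these sets. The tables of section 7.1.1 cover events outside it, but without a stated grade or select grouping.

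**2. What the planned rate estimates.** For one select category, let *a* be the proportion of patients with an event of that type, and *s* the proportion of those patients with at least one such event marked as related. Then:

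- reported rate = *a* × *s*
- ratio of reported rates in two subgroups = (*a*₁/*a*₂) × (*s*₁/*s*₂)

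The subgroup comparison reflects the events alone only if *s*₁ = *s*₂. The protocol gives no information on *s*, and the related-only tables cannot supply it. A table by event term irrespective of causality estimates *a* directly, and with the related-only table it also shows *s*.

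**3. The protocol's own evidence on attribution.** Inputs from section 1.1: patients in the cited double-blind trial with grade 3-4 events that investigators considered related to the trial regimen.

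| Arm | Count | Rate | Exact 95% CI | Printed |
|---|---|---|---|---|
| Nivolumab | 71/532 | 13.3% | 10.6 to 16.5 | 13% |
| Placebo | 15/260 | 5.8% | 3.3 to 9.3 | 6% |

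Both printed figures are reproduced.

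- Ratio, placebo to nivolumab: 0.0577 / 0.1335 = 0.43 (95% CI 0.25 to 0.74, log scale).
- Difference: 13.3% − 5.8% = 7.6 points before rounding (95% CI 3.5 to 11.6, Wald).

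Investigators thus attributed severe events to the regimen in patients who were not receiving the drug. This shows that attribution is imperfect. It is not an estimate of *s*, and it does not concern drug-caused events marked as not related.

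**4. The comparison window.** Related events are collected without limit and non-related events only to 100 days after the last dose, so the two can be combined fairly only up to that limit. Section 7.1.1 starts collection at consent, and section 3.1 allows enrollment before the first dose, so the window needs an explicit start at first dose.

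**The case against.** **Related-only analysis fits the objective.** Section 2.2 asks for incidence and severity of AEs in relation to nivolumab, and section 4.1.3.5 is headed accordingly. This stands: the plan does not contradict itself.

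**That non-related AEs go ungraded is partly inferred from silence.** Section 4.1.3.5 does not say that only related events are graded, and section 4.1.1 leaves table shells to the SAP, which is not shown. Non-related events are also classified for seriousness and reported. This stands in part. Seriousness is not a severity grade, however, and the select-AE definition is fixed by the protocol itself. Section 6 requires the SAP only before database lock, when a grade never captured at the site may be hard to recover.

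**The placebo figure points the other way.** It shows over-attribution under blinding, whereas the events lost from the select tables would be under-attributed. This stands. A reader might apply the cited rates to 314 patients and expect about 42 with a related grade 3-4 event (314 × 0.1335), of which about 18 (314 × 0.0577) are spurious. The documents do not support that. The rates come from a blinded trial, routine open-label attribution may differ, and an all-cause table would add background events without removing wrongly attributed ones.

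**A reader might also infer that rates are not comparable across sites or countries.** The documents give no between-site or between-country data on attribution. What follows is only that such comparisons are confounded with attribution practice to an unknown degree.

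**Collection burden.** Section 5.1 limits collection to variables that serve the objectives. A grade on non-related events is a real addition if it is not already captured, but it is one field on records already required.

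**Conclusion.** The point holds as a weak analysis choice with an inexpensive remedy. By the protocol's definitions, the select-AE rates and the only severity grading it commits to are conditional on a physician's causality judgement. In a single-arm study that undercuts the stated aim of the select grouping and confounds the CheckMate 577-like comparison with attribution practice.

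The size and direction of the effect are unknown. The 5.8% against 13.3% in the cited trial shows that attribution is imperfect; it does not measure error in this study. That attribution differs between the trial-like and other patients is plausible, but it is an assumption.

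The denominator is a minor, separate matter. Enrollment may precede the first dose and the data set is defined by eligibility, so total patients could include some who were never treated. The study population is described elsewhere as patients initiating nivolumab, so a dosed denominator is probably intended and only needs to be stated.

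**What to change.** In sections 3.5.1.4 and 4.1.3.5:

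1. Define the select-AE categories by event term, irrespective of causality.
2. Record a severity grade for every collected AE.
3. Tabulate all-cause select AEs, and all AEs by grade, with onset from first dose to 100 days after the last dose, overall and for the CheckMate 577-like comparison.
4. Keep the related-only tables alongside; they answer the stated objective.
5. State that AE incidence is calculated among patients who received at least one dose of nivolumab.

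The cost is a few more tables and, if not already captured, a grade field on non-related AEs. No new events need to be collected, because non-related AEs are already reported over this window. The grade field should be settled while sites are still entering data.

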# 4.1.4 Analysis Plan for Exploratory Objectives

PRO analysis of patient satisfaction with nivolumab treatment will be assessed using CTSQ and FACT-G7 instrument. CTSQ scores results overall and for each of the three domains: Expectations of Therapy (five items), Feelings about Side Effects (four items), and Satisfaction with Therapy (seven items) will be summarized using standard descriptive statistics (see Section 4.1.2). The FACT-G7 will include items GP1 "I have lack of energy", GP2 "I have pain", GP3 "I have nausea", GP4 "I worry that my condition will get worse", GP5 "I am sleeping well", GP6 "I am able to enjoy my life", and GP7 "I am content with the quality of my life right now", and will be summarized using standard descriptive statistics (see Section 4.1.2).

Data will be recorded at Day 0, and Months 3, 6, 9, and 12 (counted relative to treatment initiation). Mean change from Day 0 to assessment points throughout the study will be evaluated. At each timepoint for analysis, the number of patients who completed the patient satisfaction questionnaire and the FACT-G7 will be reported as a percentage of eligible patients.

## 4.2 Sample Size

The sample size calculation is based on the primary outcome of the study and has been calculated assuming a 40% DFS rate after two years of follow-up and with an absolute precision of 7% for a sample size of 314 patients (to account for 10% drop-out). These calculations are based on assumptions from the CheckMate577 trial.

DFS rate (%)	Absolute precision (%)	Ν	N (Considering 10% drop-out rate)
	6%	685	754
20%	7%	504	555
	8%	385	424
	6%	526	579
30%	7%	387	426
	8%	296	326
40%	6%	386	425
	7%	285	314
	8%	217	239
50%	6%	268	295
	7%	197	217
	8%	151	167

Table 7: Sample Sizes and Absolute Rates (%)

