routinely collected during disease management in clinical practice. This study is strictly observational, and prescriptions of nivolumab will be at the sole discretion of the treating physician. The overall study duration will be up to 42 months with an enrollment period of 18 months. Data will be collected by sites at Day 0 (baseline) and month 3 (M3), M6, M9, M12, M18, M24, M30, M36, and M42. Follow-up time for the first patient in will be up to 42 months and a minimum of 24 months for the last patient in. Patients will be followed until the end of study period, death, lost to follow-up, or study withdrawal, whichever comes first.

**Study Population:** Adult subjects diagnosed with early-stage EC/GEJC initiating nivolumab treatment per the clinical care recommendation of their treating physician and meeting the following inclusion criteria and none of the exclusion criteria will be eligible to participate in the study:

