#### Exploratory outcomes

• Treatment satisfaction prior to and after nivolumab treatment initiation and health related quality of life (HR-QoL) outcomes.

*Interim analysis:* There will be three interim analyses conducted in accordance with the scientific committee of the study.

**Sample Size/Power:** The sample size calculation is based on the primary outcome of the study and has been calculated assuming a 40% DFS rate after two years of follow-up and with an absolute precision of

7% for a sample size of 314 patients (accounting for a 10% drop-out rate). These calculations are based on assumptions from the CheckMate577 trial.

**Limitations/Strengths:** Although all possible measures will be taken to ensure quality and robustness of the data collected, there are some limitations that are inherent to the observational nature of this study including selection bias, attrition bias, and variability in local treatment practices, guidelines, and data quality across sites. Notably, selection bias due to non-consent will be mitigated by providing clear information to patients and physicians on the importance of the study and low burden of participation. Furthermore, the use of a large diverse sample of patients and prescribers from the US and Germany will contribute to the generalizability of the results. The site selection process will ensure that the sites participating are representative of the US and German landscape of EC or GEJC treatment.

Findings from this study will help support results from previous clinical trials and generate real-world effectiveness data in patients initiating nivolumab for the treatment of EC/GEJC. This study will provide a better understanding of the demographics, patterns of care, and clinical outcomes of patients with EC/GEJC treated with nivolumab in routine clinical practice and will be used to inform key stakeholders, patients, healthcare practitioners, guideline committees, and regulatory authorities.

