### 4.1.1.2 Time-to-Event Analyses

Time-to-event analysis will be used for outcomes that assess the length of time until the occurrence of a predefined outcome. The following time-to-event outcomes defined in Section 3.5.1 will be analyzed for all nivolumab patients, for patients that receive subsequent(s) treatments following nivolumab, and by subgroup of interests if sample size allows:

- DFS
- OS
- PFS2
- DMFS
- PRS

The time-to-event for each outcome during the study period will be reported in months, and summarized descriptively (minimum, median, quartiles, and maximum). Kaplan-Meier (KM) curves will be used to illustrate the survival probability estimates and the number of patients at risk over time for the overall population and by subgroup of interests when relevant. Median survival time estimates and survival probabilities (with two-sided 95% CIs) at each study period timepoint will be provided.

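### Table 7 does not follow from its stated precision: ±7 points at a 40% DFS rate needs about 189 evaluable patients, not 285, and the planned 314 give about ±5.7 points

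*Protocol*

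**What the plan says.** Protocol Section 4.2 bases the sample size on the primary outcome, "assuming a 40% DFS rate after two years of follow-up and with an absolute precision of 7% for a sample size of 314 patients". It adds that the number is set "to account for 10% drop-out". The synopsis, under Sample Size/Power, repeats it: "7% for a sample size of 314 patients (accounting for a 10% drop-out rate".

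Table 7 lists N for two-year DFS rates of 20%, 30%, 40% and 50% at absolute precisions of 6%, 7% and 8%, with a second column for 10% drop-out. The chosen row (40%, 7%) reads 285 before drop-out and 314 after.

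Section 4.2 gives no formula and no confidence level. Section 4.1.1.2 plans that "survival probabilities (with two-sided 95% CIs) at each study period timepoint will be provided". Section 4.1.1 states: "This study is purely descriptive, and no formal hypotheses will be tested". The calculation is therefore about precision for a single cohort, with no power involved. The synopsis gives follow-up as "a minimum of 24 months for the last patient in".

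**The concern.** For a fixed absolute half-width, the N needed to estimate a proportion is proportional to p(1−p), which is largest at 50%. Table 7 runs the other way. At ±7 points it asks for 504 patients at 20%, 387 at 30%, 285 at 40% and 197 at 50%. If 197 are enough at 50%, where the variance is greatest, 285 cannot be required at 40%.

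This is the protocol's only justification of the sample size. Section 5.1 (attrition bias) warns that the target precision may be missed if loss to follow-up is not negligible. Read with Table 7, that happens below 285 evaluable patients; the correct threshold is 189. Section 5.1 also provides for longer enrolment or a higher maximum per site if recruitment falls short, and that decision would be judged against a threshold that is too high. The table also makes N look very sensitive to the assumed rate, with 314 at 40% against 217 at 50%, when it is nearly flat in that range.

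**Working it through.** **Inputs.** p = 0.40, d = 0.07, drop-out 10%, N = 285 and 314 (Section 4.2 and Table 7). z = 1.96 for two-sided 95%; this is an assumption for Section 4.2, taken from Section 4.1.1.2. There is no planned administrative censoring before 24 months (synopsis), so the Greenwood variance of the 24-month Kaplan-Meier estimate reduces to p(1−p)/N if nobody is censored earlier.

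**Attempt to reproduce 285.** N = z² p(1−p) / d² = 3.8416 × 0.24 / 0.0049 = 188.2, so 189. The figure of 285 is not reproduced.

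**Half-width from the stated numbers at 40%.** 1.96 × √(0.24/N):
- N = 285: ±5.69 points
- N = 283 (314 × 0.90 = 282.6): ±5.71 points
- N = 314: ±5.42 points

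**All twelve rows.** The last two columns are the correct N and that N divided by 0.90, each rounded up.

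| DFS rate | d | Table 7 N | Table 7 with drop-out | z²p(1−p)/d² | Divided by 0.90 |
|---|---|---|---|---|---|
| 20% | 6% | 685 | 754 | 171 | 190 |
| 20% | 7% | 504 | 555 | 126 | 140 |
| 20% | 8% | 385 | 424 | 97 | 108 |
| 30% | 6% | 526 | 579 | 225 | 250 |
| 30% | 7% | 387 | 426 | 165 | 184 |
| 30% | 8% | 296 | 326 | 127 | 142 |
| 40% | 6% | 386 | 425 | 257 | 286 |
| 40% | 7% | 285 | 314 | 189 | 210 |
| 40% | 8% | 217 | 239 | 145 | 162 |
| 50% | 6% | 268 | 295 | 267 | 297 |
| 50% | 7% | 197 | 217 | 196 | 218 |
| 50% | 8% | 151 | 167 | 151 | 168 |

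The three 50% rows agree to within one patient. The other nine do not.

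**Other interval methods for the 40%/7% row.** Continuity-corrected Wald 203, Clopper-Pearson 200 to 209, Wilson 185, log-log Kaplan-Meier 187 to 189, exponential-model survival estimate 176. None is near 285.

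**Other confidence levels for the same row.** Two-sided 90% (or one-sided 95%) gives 133, two-sided 98% gives 266 and two-sided 99% gives 325. Back-solving the 7% rows, the implied two-sided level is about 99.99% at 20%, 99.7% at 30%, 98.4% at 40% and 95% at 50%. No single level explains the table.

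**Censoring.** To explain the 7% rows, censoring would have to remove 1 − 126/504 = 75% of the information at 20%, 1 − 189/285 = 34% at 40% and almost none at 50%. Drop-out is already added in its own column.

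**Likely source.** Replacing p(1−p) by (1−p)² gives 1.96² × 0.36 / 0.0049 = 282.2, so 283 for the chosen row, and it matches all twelve rows to within 3 patients. The two expressions are equal only at p = 0.5, which is why only those rows are right. This source is an inference; the mismatch does not depend on it.

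**Drop-out column.** Every cell is N × 1.10 rounded up, for example 285 × 1.10 = 313.5, so 314. To retain N after 10% loss the divisor is 0.90: 285/0.90 = 316.7, so 317. The shortfall is 3 patients in the chosen row and at most 8 (685/0.90 gives 762 against 754).

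**The case against.** The strongest reply is that the error does no harm to the study's aim. It is conservative: about 283 evaluable patients comfortably meet ±7 points, which need 189. Nothing is tested, so no power or decision is at risk, and no row of Table 7 gives too few patients before drop-out by more than rounding. This stands, and it limits the seriousness: the protocol misstates its precision, but the study is not underpowered or too small. The drop-out slip is likewise minor, because 314 exceeds the corrected enrolment of 210. The protocol does not say that other rows of Table 7 would be used for re-planning, so harm by that route is only possible.

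Section 4.2 also names no confidence level, so 95% is imported. That is true, but no common level gives 285 and no single level fits the table.

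The ±5.7 is itself approximate. Kaplan-Meier uses the partial follow-up of drop-outs, which moves the half-width towards ±5.4. In the other direction, Section 3.1 gives the last patient up to 24 months where the synopsis gives a minimum of 24, no visits are mandatory, and data collection has a window of ±15 days. Late entrants could be censored just before 24 months, which would widen the interval. These conditions belong in the restated sentence.

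Finally, the 40% may be low. The median of 22.4 months quoted in Section 1.1 for the nivolumab arm of CheckMate 577 implies 0.5^(24/22.4) = 47.6% at 24 months if DFS is exponential (an assumption). At that rate ±7 points needs 196 and 283 evaluable patients give ±5.8, so the conclusion barely changes.

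**Conclusion.** The concern holds. The rate, precision and sample size stated in Section 4.2 and the synopsis are mutually inconsistent, and nine of the twelve N values in Table 7 are wrong. At a 40% two-year DFS rate, ±7 points needs 189 evaluable patients (210 enrolled), against the stated 285 (314 enrolled). The planned 314 give about ±5.7 points with 283 evaluable, or ±5.4 if all are observed to 24 months. On the same count, ±7 points would survive the loss of 125 of 314 patients (39.8%), far more than Table 7 suggests.

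This rests on a two-sided 95% level, on reading absolute precision as the half-width of the interval, and on negligible censoring before 24 months other than the stated drop-out. The error makes the study larger than its stated target requires; it does not leave it short of precision.

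**What to change.** Keep 314. In Section 4.2 and the synopsis, replace the precision statement with wording such as: *314 enrolled patients, about 283 evaluable after 10% drop-out, give a two-sided 95% confidence interval with a half-width of about 5.7 percentage points for a 24-month DFS rate of 40%, assuming the remaining patients are observed to 24 months or to an earlier event.*

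Recompute Table 7 from z²p(1−p)/d², with formula and confidence level stated and drop-out applied by dividing by 0.90; the last two columns of the table above can be used directly.

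Two related edits belong in the same revision. The calculation concerns the 24-month DFS rate, whereas the primary analysis in Section 4.1.2 reports median DFS, so the sentence should name the quantity whose precision it gives. The minimum follow-up of the last patient should read the same in the synopsis and Section 3.1, because the calculation relies on it.

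The cost is one sentence in two places, one table and these two wording edits, with no change in enrolment, data collection or analysis.
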